## 9.8.1. Pre-Hospital Discharge

The following electrical testing will be performed using the implanted IPG and the device programmer:

### Pacing Capture Thresholds (PCT) / Sensing / Impedance measurements

- Perform a manual HB and RV PCT at 0.5ms and 1.0ms and print threshold test strips
- Document R wave and impedance results

### 12 Lead EKG rhythm strip

- Print 12 lead EKG rhythm strip capturing presenting rhythm, intrinsic rhythm, PCTs at 0.5ms, PCTs at 1.0ms and while pacing at final device programmed outputs and document QRS duration for each

### Other Data Collection

- Final device interrogate ALL and Save to Media
- Adverse Events
- Study deviations
- Device Deficiencies

## 9.8.2. Cardiac CT Scan

The following data will be collected during the Cardiac CT Scan.

- Cardiac CT Scan with contrast focusing on RA and RV chambers

## 9.8.3. 1 week, 6 month and 12 month visit

The following electrical testing will be performed using the implanted IPG and the device programmer. In addition, a DR220 Holter monitor will be used at the 1 week visit. The DR220 Holter monitor will also be used at the 6 month visit if missed at the 3 month visit.

### Pacing Capture Thresholds (PCT) / Sensing / Impedance measurements

- Perform a manual HB and RV PCT at 0.5ms and 1.0ms and print threshold test strips
- Document R wave and impedance results

### 12 Lead EKG rhythm strip

- Print 12 lead EKG rhythm strip capturing presenting rhythm, intrinsic rhythm, PCTs at 0.5ms, PCTs at 1.0ms and while pacing at final device programmed outputs and document QRS duration for each

### Other Data Collection

- Final device interrogate ALL and Save to Media
- Adverse Events
- Study deviations
- Device Deficiencies

## 9.8.4. 3 month visit

The following electrical testing will be performed using the implanted IPG and the device programmer. In addition, a second DR220 Holter monitor will be used at the 3 month visit (if not able to collect at this visit, collect at the 6 month visit).

### Pacing Capture Thresholds (PCT) / Sensing / Impedance measurements

- Selective HBP patients
  - Perform a manual HB PCT at 0.1 (or 0.12) ms; 0.2 (or 0.21) ms; 0.5 (or 0.52) ms; 0.76 (or 0.8) ms ; 1.0 ms; and 1.5 ms and print test results
  - Perform a manual RV PCT at 0.5ms and 1.0ms and print threshold test strips
  - Document R wave and impedance results
- Non-Selective HBP patients
  - Perform a manual HB and RV PCT at 0.5ms and 1.0ms and print threshold test strips
  - Document R wave and impedance results

## 12 Lead EKG rhythm strip

- Print 12 lead EKG rhythm strip capturing presenting rhythm, intrinsic rhythm, at all PCTs and while pacing at final device programmed outputs and document QRS duration for each

## Other Data Collection

- Final device interrogate ALL and Save to Media
- Adverse Events
- Study deviations
- Device Deficiencies

## 9.9. Device Interrogation / Save-to-Media

For the implant and follow-up visits, a final “Interrogate ALL” device interrogation file (.pdd) must be obtained and saved in a digital format (Save-to-Media). Store one copy of the save-to-media at the site and send a copy to Medtronic. Do not clear device data.

A device interrogation (final “Interrogate ALL”) and Save-to-Media should also be completed at the time of study exit, system modification and in the case of a death (where possible).

## 9.10. System Modification

A system modification CRF will be completed in the event the device and/or lead(s) require invasive modification (e.g. generator or lead explant, generator or lead replacement, lead repositioning). In the event of a system modification, regardless of outcome of the modification, the follow-up visit schedule for the subject will remain unchanged. For a system modification, the following information/activities are required to be collected:

- Modification or replace/explant date
- Reason for modification
- Information on device or lead modified
- Information on any replacement device or lead(s)
- SelectSecure™ MRI SureScan™ Model 3830 Pacing Capture Thresholds at 0.5ms and 1.0ms
- Final System Configuration
- Initial and Final device interrogate ALL and save-to-media
- Adverse Events
- Study deviations
- Device Deficiencies

It is recommended that all explanted Medtronic products (device, leads, etc.) are returned to Medtronic for analysis per local process and when permissible by local laws and regulations.

In the event that a subject has a re-attempt after a previous unsuccessful system modification, the subsequent attempt(s) must be reported via CRF as separate system modifications.

## 9.11. Subject Withdrawal or Discontinuation

Study exit is defined as the moment when a subject officially stops participating in the study. From that moment onward no data will be collected from the subject. The date and the reason for exiting the subject must be reported to Medtronic at the earliest opportunity.

Subjects will be exited from the study for any of the following situations:

- Study completed
- Subject does not have an implant of a SelectSecure™ MRI SureScan™ 3830 lead for His bundle pacing
- Subject death
- Subject lost to follow-up
- Subject did not meet eligibility criteria
- Subject chooses to exit
- Investigator withdraws subject

If possible, the following procedures should be performed / data collected at the exit visit:

- Report the reason for exit
- Final interrogate ALL and save-to-media file for exits occurring prior to the 12 month visit
- Adverse Events
- Study deviations
- Device Deficiencies

Following exit, subjects will continue to receive standard medical care. There will be no further required study-related follow-up visits for these subjects. All data through the time of the subject's exit will be available for data analyses.

### 9.11.1. **Lost to Follow-up**

In the case that the subject is determined to be lost to follow-up, details of a minimum of two attempts and the method of attempt (e.g., one letter and one phone record or two letters) to contact the subject must be recorded. In addition, follow the regulations set forth by the governing IRB.

### 9.11.2. **Subject chooses to exit (i.e. revokes informed consent)**

A subject can withdraw from the study at any time. If the subject wishes to exit from the study (i.e. the subject revokes informed consent), the site is required to document the reason for exit on the Study Exit eCRF. In addition, study sites shall follow the regulations set forth by the governing IRB. If possible, the following data should be collected prior to subject withdrawal:

- Report the reason for the subject withdrawal
- Final device interrogation/save-to-media
- Adverse Events
- Study deviations
- Device deficiencies

### 9.11.3. **Investigator Withdraws Subject**

No subjects should be withdrawn by investigators unless compelling medical justification is present. It is recommended investigators discuss any withdrawals with the study sponsor prior to exiting subjects. If an Investigator withdrawal is necessary, the following data should be collected prior to subject withdrawal if possible:

- Report the reason for subject withdrawal
- Final device interrogation/save-to-media
- Adverse Events
- Study deviations
- Device deficiencies

## 9.12. **Assessment of Safety**

Device Deficiencies and Adverse Events related to the procedure or Medtronic SelectSecure™ MRI SureScan™ Model 3830 pacing lead for His bundle pacing will be collected. In addition, all SAEs that result in death will be collected. Further information on the collection and assessment of Adverse Events is discussed in Section 11.

## 9.13. Recording Data

The study will collect data using Oracle Clinical, an electronic data management system for clinical studies. Sites will enter data onto electronic case report forms (eCRFs) within the Oracle Clinical database.

Data reported on the eCRFs shall be derived from source documents, which may include worksheets, patient medical records, EP Recording system printouts, 12 lead EKG, Device interrogation files, fluoroscopy image files, and programmer threshold test printouts. These source documents must be created and maintained by the clinical research study site team. Further detail on data management is provided in Section 15.2.

## 9.14. Deviation Handling

A deviation is defined as an event in which the investigator or site personnel did not conduct the study according to the Clinical Investigational Plan (CIP) or applicable laws and regulations. Every attempt must be made to avoid deviations.

In the event the investigator deviates from the CIP to protect the life or physical well-being of a subject in an emergency, the investigator shall notify the sponsor and reviewing IRB within 5 working days after the emergency occurred.

Except in such an emergency, prior approval by the sponsor is required for changes in or deviations from the CIP. Prior approval is not expected in situations where unforeseen circumstance is beyond the investigator's control.

Medtronic will be responsible for documenting and analyzing deviations, assessing their significance, and identifying any necessary corrective and/or preventive action. All deviations will be recorded on the Protocol Deviation Case Report Form. Medtronic will provide site-specific reports to investigators summarizing information on deviations that occurred at the investigational site on a periodic basis.

# 10. Risks and Benefits

## 10.1. Potential Risks

Medtronic follows rigorous Quality Assurance and Control procedures throughout the life of a product, from the business analysis phase through development, market release, and post-market surveillance.

All devices used in the IMAGE-HBP study will be commercially released and used in accordance with their approved labeling. The safety and clinical performance of these devices have been demonstrated through previous-pre-clinical testing and previous clinical studies.

# Imaging Study of Lead Implant for His Bundle Pacing Clinical Investigation Plan

056-F275

Version 4.0

Page 35 of 57

Medtronic

Subjects who are pregnant may be at increased risk (e.g. radiation exposure and other unforeseen risk to the fetus), and are excluded from participation in the study. If a subject becomes pregnant during the study, she must notify the physician immediately. The subject will remain in the study for analysis, but the investigator will avoid any procedures that may be determined harmful.

Incremental risks for participating in this study may include the following risks associated with the additional procedures listed below:

- Risk associated with Fluoroscopy exposure
  - During the implant procedure, additional cine recordings will be collected at the final lead fixation location. The duration of the extra radiation exposure is expected to be less than 5 minutes of incremental time beyond what would be experienced during a standard implant procedure.
- Risk associated with Cardiac CT Scans
  - Exposure to radiation from one test is similar to the amount of radiation you are naturally exposed to over one to five years.
  - The Cardiac CT Scan may detect an incidental finding, which is something that doesn't cause symptoms now but may require more tests after being found.
  - Allergic reaction to contrast used during the Cardiac CT Scan

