## 10.2. Potential Benefits

There may be no direct benefit to the subject from participating in this study. The benefits of receiving a lead implant for His bundle pacing are the same if the patient participates in the study or not.

The Cardiac CT Scan performed in this study is not for diagnostic purposes. However, any potential abnormalities that are identified by the site investigator will be relayed to the subject with instruction for medical follow up.

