### 11.1. Adverse Events

Adverse Event (AE) definitions are provided in **Table 4**. The following AEs will be collected throughout the study duration:

- All AEs related to the Medtronic SelectSecure™ MRI SureScan™ model 3830 lead for His bundle pacing
- Procedure related AEs related to the Medtronic SelectSecure™ MRI SureScan™ model 3830 lead for His bundle pacing
- SAEs resulting in subject death

Events should be reported for the procedure or the lead for His bundle pacing that are considered to be possibly related, probably related or have a causal relationship.

Reporting of these events to Medtronic will occur on an AE eCRF, including date of AE, treatment, resolution, assessment of both the seriousness of the AE and the relatedness to the product. Each AE must be recorded on a separate AE eCRF. Documented pre-existing conditions are not considered AEs unless the nature or severity of the condition has worsened.

For AEs that require immediate reporting (see **Table 6**), initial reporting may be done by phone, email or on the eCRF completing as much information as possible. The original completed AE eCRF must be submitted to Medtronic as soon as possible.

Any medication, whether cardiovascular or not, associated with the treatment of an AE must be reported. Medication changes that are not related to adverse events will not be collected.

Subject deaths are also required to be reported. Refer to Section 11.6 for Subject Death collection and reporting requirements.

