# Imaging Study of Lead Implant for His Bundle Pacing Clinical Investigation Plan

056-F275

Version 4.0

Page 38 of 57

Medtronic

Lead for His bundle pacing Related	An adverse event that results from the presence or performance (intended or otherwise) of the lead for HBP
Procedure Related	
An Adverse Event that is directly related to the implantation or surgical modification of the lead for His bundle pacing.
 
NOTE: In general, this excludes events that are inherent to any surgical procedure (e.g. anesthesia complications) as well as indirect subsequent consequences of the procedure (e.g. reaction to pain medication).

Not Related	
Relationship to the device or procedures can be excluded when:
 

• The event is not a known side effect of the product category the device belongs to or of similar devices and procedures;

• The event has no temporal relationship with the use of the investigational device or the procedures;

• The serious event does not follow a known response pattern to the medical device (if the response pattern is previously known) and is biologically implausible;

• The discontinuation of medical device application or the reduction of the level of activation/exposure – when clinically feasible – and reintroduction of its use (or increase of the level of activation/exposure), do not impact on the serious event;

• The event involves a body-site or an organ not expected to be affected by the device or procedure;

• The serious event can be attributed to another cause (e.g. an underlying or concurrent illness/clinical condition, an effect of another device, drug, treatment or other risk factors);

• The event does not depend on a false result given by the investigational device used for diagnosis, when applicable;

• Harms to the subject are not clearly due to use error;

• In order to establish the non-relatedness, not all the criteria listed above might be met at the same time, depending on the type of device/procedures and the serious event.

 
*The study will not be collecting AEs that are not related to the lead for His bundle pacing

---

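### Non-fatal harms of the study-only contrast cardiac CT fall outside the adverse event collection rules, although Protocol Section 10.1 names contrast allergy as an added risk of taking part

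*Protocol*

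**What the plan says.** **The scan and its risk.** Protocol Section 6 sends every subject who receives the lead for a cardiac CT. Section 9.8.2 describes it as "Cardiac CT Scan with contrast focusing on RA and RV chambers". Section 10.2 states: "The Cardiac CT Scan performed in this study is not for diagnostic purposes". Section 10.1 opens its list with "Incremental risks for participating in this study may include the following risks associated with the additional procedures listed below", and under the CT it names radiation, incidental findings and "Allergic reaction to contrast used during the Cardiac CT Scan".

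**What is collected.** Section 11.1 lists three kinds of event:
- any event attributed to the Model 3830 lead;
- a procedure group, worded as "Procedure related AEs related to the Medtronic SelectSecure™ MRI SureScan™ model 3830 lead for His bundle pacing";
- fatal serious events, whatever their cause.

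The Synopsis (Safety Assessments), Section 9.12 and Section 11.5.1 repeat this scope. Table 4 defines a procedure-related event as one directly "related to the implantation or surgical modification of the lead for His bundle pacing". Notes in the same table say that events unrelated, or unlikely to be related, to the lead are not collected, and that the only serious events collected are those that led to death.

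**How events are classified and reported.** Table 5 offers two relatedness parameters, the lead and the procedure. SAP Section 7.9.6 characterizes the events the study has collected, in a table with lead-related and procedure-related columns only.

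**The concern.** The CT is done for the study and not for the subject's care, so a reaction to its contrast is a harm that participation adds. The sponsor foresaw that harm and wrote it down as a risk, but the collection rules then leave it out unless it is fatal.

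What is at stake is subject-safety reporting. Section 10.3 says the identified risks have been mitigated and that the residual risk is acceptable. For non-fatal CT harms the trial's own data could not be set against that statement. Section 12 says there is no data management or clinical events committee, so no such body is in place to pick up what the event forms leave out. No efficacy or lead-performance estimate is involved.

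**Working it through.** No figure in the plan describes CT harms, so the main check is to test one event against each rule. The test event is a non-fatal allergic reaction to contrast at the study CT, serious or not.

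| Rule | Does the event qualify? |
|---|---|
| Section 11.1, lead-related events | No. Table 4 requires the event to result from the presence or performance of the lead. |
| Section 11.1, procedure events tied to the lead | No. Table 4 limits these to implanting or surgically modifying the lead, and a CT is neither. |
| Section 11.1, serious events resulting in death | No, because the event is non-fatal. A fatal reaction would qualify, with no relatedness condition. |
| Table 4 notes on unrelated and unlikely events | Expressly not collected when unrelated, or unlikely to be related, to the lead. |
| Table 4 note on serious events | Only fatal ones are collected. |

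The last note is not needed for the result. Read literally, it would also drop non-fatal serious events related to the lead, which Section 11.1 collects and Table 6 requires to be reported. It needs aligning in any case. The Section 11.1 list and the procedure-related definition are enough to exclude the CT event.

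**Does anything later recover it?**
- Section 9.8.2 lists CT images only. Sections 9.8.1, 9.8.3 and 9.8.4 each carry an adverse events item.
- Table 5 has no CT option. Table 4 grades an event as possibly related when relatedness cannot be assessed, so an ambiguous event might be recorded. It would then be filed under the lead or the procedure and could not be counted as a CT event.
- SAP Section 7.9.6 works from collected events and adds no CT category.
- Deaths are recovered: Protocol Section 11.6.1 puts every death on an event form, and SAP Section 7.9.9 lists deaths for all enrolled subjects.

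**Illustrative size.** Inputs:
- Number of scans: Protocol Section 13.1.3 plans 62 implant attempts (SAP Section 6, written from protocol version 2.0, still has 50). The CT follows receipt of the lead, not the success criterion, so 62 is the upper end. Taking 0.9 × 62 = 55.8, about 56, gives a lower working value. It borrows the assumed success proportion, and a subject whose lead misses the threshold criterion would still be scanned.
- Reaction rate *r*: not in the documents. I assume 0.5% to 3%.

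Expected events = *n* × *r*. Chance of at least one = 1 − (1 − *r*)^*n*.

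| Scans | *r* | Expected events | Chance of at least one |
|---|---|---|---|
| 56 | 0.5% | 56 × 0.005 = 0.28 | 1 − 0.995^56 = 0.245 |
| 56 | 3% | 56 × 0.03 = 1.68 | 1 − 0.97^56 = 0.818 |
| 62 | 0.5% | 62 × 0.005 = 0.31 | 1 − 0.995^62 = 0.267 |
| 62 | 3% | 62 × 0.03 = 1.86 | 1 − 0.97^62 = 0.849 |

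These values follow entirely from the assumed rate.

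**The case against.** **The plan is looser elsewhere.** Section 9.4 tells sites to report adverse events and deaths after consent, without qualification. Table 2 lists the CT as a study procedure and has adverse events recorded as they occur. The causal-relationship grade in Table 4 speaks of the device or study procedures, and the general definition of an adverse event covers the procedures involved. The CT window in Table 3 (days 0 to 17) overlaps the pre-discharge and 1-week visits, where adverse events are listed. A site could read all this as covering the CT. This stands as evidence of inconsistency, and some sites might record a reaction. It does not override the specific rules: the first two passages govern timing, the third grades causality, and the definition says what an adverse event is, not which ones are collected.

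**Other reporting routes exist.** Sections 11.5.1 and 11.5.2 hold investigators to IRB and local requirements. A serious reaction may reach an IRB that way, but that does not place it in the trial database. SAP Section 7.9.6 also reports events in subjects with no implant attempt, which hints at wider collection. Those subjects do not receive the CT.

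**Narrow collection is deliberate.** The products are market released, no objective concerns CT safety, and subjects with a contraindication to CT are excluded. All true. The lead's market status does not bear on a scan added for the study, however, and the sponsor still lists contrast allergy as a risk after that exclusion.

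**Stronger readings that the documents do not support.** A reader might infer that all CT harm goes unrecorded; deaths are collected. A reader might take the CT as the only added procedure; Section 10.1 also lists extra cine imaging, which happens during the implant and whose harms could be judged procedure related. A reader might expect collection to reveal a problem at one site. At up to 5 sites, 56 / 5 is about 11 scans each, or 11.2 × 0.005 = 0.06 to 11.2 × 0.03 = 0.34 expected events, too few for that.

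**Conclusion.** The point holds for non-fatal harms of the study CT, including a non-fatal serious contrast reaction. They are excluded by stated rules, not left out for want of detail, and neither Table 5 nor the SAP table brings them back. As written, the database cannot report their frequency.

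The conclusion rests on reading the specific collection rules as governing the more general wording. If that reading is disputed, sites will differ in what they record, and the same passages still have to be reconciled.

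The likely count is small: about 0.3 to 1.9 events over 56 to 62 scans at an assumed 0.5% to 3%. Collecting them would not give a precise rate. With no events in 56 scans, the one-sided 95% upper bound is 1 − 0.05^(1/56) = 5.2%, above the whole assumed range. The gain is that any reaction which occurs is recorded and attributed to the CT. The change should be made on subject-safety grounds. The primary endpoint, its confidence interval and the sample size are unaffected.

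**What to change.** - **Protocol Section 11.1:** add a collected category, *AEs related to the study-required cardiac CT, including contrast*, with matching words in the Synopsis and Sections 9.12 and 11.5.1.
- **Table 4:** align the notes on events not collected, and the note limiting serious events to deaths, with the new category.
- **Table 5:** add study CT as a relatedness option, and carry it to the event form.
- **Section 9.8.2:** add an adverse events item, as the other visit sections have.
- **Section 9.4, Table 2 and the causality grades in Table 4:** reconcile with Section 11.1 so that sites read one scope.
- **SAP Section 7.9.6:** report CT-related events in their own table, outside the Secondary Objective #5 complication rate, so that the lead and procedure estimate keeps its meaning.

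The cost is a short protocol amendment with IRB approval, one more choice on an existing form, one SAP table and a few more event forms. It needs no extra visits. The cine imaging needs no separate category on this argument, since it takes place within the implant.
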